The DSMB will have the authority to temporarily or permanently discontinue the trial if it perceives that harm is occurring due to the intervention. The DSMB will meet with the internal DSMC yearly to review adverse event reports, patient complaints if any, and enrollment rates. Data will be provided at these meetings by the investigators on key variables that may indicate harm (e.g., changes in self-report scores). The DSMB biostatistician will evaluate the confidentiality and integrity of the database and the procedures for recording and storing confidential files. The DSMB also will review the elements of the plan to manage emergencies.

Sample Size Determination for Proposed Analyses

For all study outcomes, Veterans will be randomly assigned (1:1) to the G-TBT and G-DST conditions. To reduce potential Type I errors, the primary outcomes of interest for Primary Aim 1 will be patient-reported IIRS, PCL, and DASS depression scores. The power analysis was calculated to be powered at 90% with a Bonferroni-corrected 1-tailed α = .0008 (.025/3 primary outcomes) to detect non-inferiority for G-TBT in comparison to the G-DSTs. Meta-analyses of group CBT for depression (McDermut, Miller, & Brown, 2001) and Group treatment for PTSD (Haagen et al., 2015; Sloan et al., 2013) found effect size estimates ranging from 0.56 (PTSD; Sloan et al., 2013) to 1.03 (depression; McDermut et al., 2001). In Veterans, Haagen et al. (2015) reported a Hedges g of 0.63. Thus, we conducted our power analysis with a conservative expected d of 0.60. Using procedures recommended by Chow, Shao, and Wang (2017) for non-inferiority designs, which utilize the pre-specified non-inferiority margin

(here prespecified as Δ d = 0) and the estimated effect in the active comparison treatment (d = 0.60), we determined that 152 participants (76 per cell) would be needed. However, this does not account for the group clustering effect.

Following Schnurr et al. (2001), we adjusted the sample size to account for potential group effects. Based on the intraclass coefficient (.025) found in the pilot G-TBT trial ([name] et al., 2018), an estimated 174 participants would be needed to adjust for potential clustering effects if groups average 8 participants. We adjusted the sample size upward 37% to adjust for potential discontinuation and 27% based on observed missing data for telehealth assessments, resulting in a final sample size of 326 participants (163 per cell).

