The continuous measures of quality of life, psychological well-being, and social reintegration are CHART (disability), CRIS and CHART (social reintegration), IIRS and V/SF-36 (quality of life and impairment), APPQ (agoraphobia, social anxiety, and interoceptive avoidance), DASS (depression, anxiety, and stress), ADIS-5 (disorder dimensional severity scales), PCL-5 (PTSD), and STICSA-Trait (cognitive and somatic anxiety). Although multiple variables will be examined, the primary outcomes of interest will be IIRS, PCL-5, and DASS depression scores. All other analyses will be conducted in an exploratory fashion to inform future studies. Parameter estimates to calculate the effect size difference will be arrived at using three-level (measurement occasions nested within participants nested within assigned treatment group) generalized mixed-effects regression models (MRM). MRM is a method of repeated measures analyses that allows for modeling of continuous and categorical independent and dependent variables and for appropriate modeling of covariance structures when observations are correlated across time and/or across group. This analytic approach fully captures variability in outcomes across multiple follow-up assessments and accounts for any potential effect of the group to which a participant is assigned and is thus preferred over methods that collapse data over time. We will calculate between-group treatment differences as the d, based on the effect of treatment condition on the intercept parameter when the model is centered on post-intervention and on the effect of treatment condition on the intercept parameter when the model is centered on month 6. We prespecified the non-inferiority margin (d) to be 0 (indicating we expected G-TBT to be at least equivalent to G-DST) and the one-sided CI for our three primary analyses at $\alpha = .0008$. In the primary analyses of outcome variables, we will covary for the baseline value of the variable of interest. We will also include the linear effect of time as well as a time by condition interaction effect to determine whether treatment differences (or lack thereof) were stable from post-intervention through the follow-up. Additional covariates (e.g. age, number of psychiatric comorbidities, race, sex, combat theatre, and number of treatment sessions) will be added to the model to adjust for putative confounding variables. Effect size CIs that do not contain 0 provide evidence in support of noninferiority for G-TBT.

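### The one-sided Bonferroni alpha is printed as .0008, but the plan's own .025/3 is .0083; the sample size matches .0083, while the primary confidence bounds would be judged at .0008

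*Combined protocol and SAP*

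**What the plan says.** Under Sample Size Determination for Proposed Analyses, the plan names three primary outcomes (IIRS, PCL and DASS depression), sets 90% power, and gives the significance level as a "Bonferroni-corrected 1-tailed α = .0008 (.025/3 primary outcomes) to detect non-inferiority for G-TBT in comparison to the G-DSTs". Using a margin of 0 and "the estimated effect in the active comparison treatment (d = 0.60), we determined that 152 participants (76 per cell) would be needed", it arrives at 76 per cell. It then inflates in two steps: "an estimated 174 participants would be needed to adjust for potential clustering effects if groups average 8 participants", and "We adjusted the sample size upward 37% to adjust for potential discontinuation and 27% based on observed missing data for telehealth assessments". The final figure is 326, or 163 per cell.

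Under Non-Inferiority Analyses (Primary Aim 1), the level appears again as "the one-sided CI for our three primary analyses at $\alpha = .0008", this time without the fraction. The same paragraph turns those bounds into the decision rule: "Effect size CIs that do not contain 0 provide evidence in support of noninferiority for G-TBT". Neither section gives .0083 or any other reason for .0008.

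**The concern.** The printed level and its printed derivation disagree by a factor of about ten. In the sample-size section a careful reader can see the slip, because the fraction stands beside the number. In the analysis section it cannot be seen, and that is the section an analyst follows to build the primary confidence bounds. If .0008 is applied, the primary claim faces a much stricter test than the sample size supports. If the analyst silently uses .0083 instead, the result departs from the written plan and can look like a relaxation of alpha after the fact.

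**Working it through.** **Inputs.** All come from the sample-size section: familywise one-sided alpha .025, three primary outcomes, power 90%, d = 0.60 (SD 1 on the d scale), margin 0, 1:1 allocation, 76 per cell, then 174 and 326 in total.

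**The quotient.** .025/3 = .00833, and .00833/.0008 = 10.4.

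**Reproducing 76 per cell.** The formula is n per arm = 2(z_α + z_.90)²/d², with z_.90 = 1.2816. It takes 0.60 as the distance between the true difference and the null.

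- α = .025/3: z = 2.394; 2(2.394 + 1.2816)²/0.36 = 75.05, rounded up to 76. This is the plan's figure.
- α = .008 (a rounded version): 75.66, also 76.
- α = .0008: z = 3.156; 2(3.156 + 1.2816)²/0.36 = 109.4, rounded up to 110.

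Solving backwards, n = 75 corresponds to α = .00836 and n = 76 to α = .00782, so only a level in that narrow range gives 76. Other readings of .0008 do not help: two-sided it gives 120, and at 80% power it gives 89 one-sided or 98 two-sided.

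**Effect on the decision rule.** The ratio of critical values is 3.156/2.394 = 1.318, so the bound lies 1.32 times further from the estimate. The bounds would be 99.92% instead of 99.17%. Familywise error for three bounds is at most 3 × .0008 = .0024, against 3 × .00833 = .025 intended.

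**Effect on power.** Power = Φ(d√(n/2) − z_α). At n = 76 per cell:

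| True distance from the null (d) | α = .025/3 | α = .0008 |
|---|---|---|
| 0.60 | 90.4% | 70.6% |
| 0.40 | 52.9% | 24.5% |
| 0.20 | 12.3% | 2.7% |
| 0 | 0.83% | 0.08% |

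**Dependence on retention, at d = 0.60.** The formula behind 326 is not printed, but 174 × 1.37/.73 = 326.5 reproduces it. The clustering factor implied by the plan is 174/152 = 1.145; the usual 1 + 7 × .025 would be 1.175.

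| Losses assumed | Effective n per cell | α = .025/3 | α = .0008 |
|---|---|---|---|
| Both planned losses | 163 × .73/1.37/1.145 = 75.9 | 90.3% | 70.5% |
| 27% missing assessments only | 163 × .73/1.175 = 101 to 163 × .73/1.145 = 104 | about 97% | 87–88% |
| None | 163/1.175 = 139 | 99.5% | about 97% |

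The first row only reverses the plan's own inflation, so it is not independent support for 76.

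**Size if .0008 were meant.** 110 per cell is 220 in total; with the plan's own inflation, 326 × 220/152 = 471.8, about 472.

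All power figures use the normal approximation for an unadjusted two-sample comparison, as in the sample-size step. Only the ratio of critical values and the range of p-values carry over to the baseline-adjusted mixed model.

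**The case against.** The strongest reply is that the power loss is overstated. The drop from 90.4% to 70.6% needs a true between-arm difference of 0.60, whereas the plan describes 0.60 as the effect in the active comparator and expects G-TBT to be at least equivalent. If the arms are equal and the margin is 0, success has a probability of 0.83% or 0.08%, and correcting alpha rescues almost nothing. This stands. How 0.60 fits a zero margin is a separate problem that the present correction does not solve.

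The loss also depends on retention. The Missing Data section keeps non-adherent participants in the study and imputes missing outcomes, so stopping treatment need not mean losing data. This stands too, which is why a range is shown above.

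It can further be said that sizing at .0083 is inferred, since the sample-size formula is not printed. That is true, but the inference is strong: .025/3 gives exactly 76, and the nearest .0008 variant tried misses by 13 per cell.

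Finally, the slip is conservative, and the fraction is printed beside it in one place. That limits the harm but does not remove it, because the decision rule carries .0008 alone. None of these points touches the wrong quotient or the p-values that would change verdict.

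**Conclusion.** The concern holds and should be fixed before the primary analysis. Two things are certain: .025/3 is .0083, and a one-sided p between .0008 and .0083 on any primary outcome passes the intended criterion but fails the printed one, whichever model produces it and whatever the retention. That the trial was sized at about .0083 is a strong inference from the 76 per cell. The power cost is conditional. At a true distance of 0.60 it is about 20 percentage points at the planned effective size (90.4% against 70.6%), about 10 points if only the 27% missing assessments are lost, and about 3 points with no loss. Type I error is not inflated.

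**What to change.** Replace .0008 with .0083 in both sections, show the fraction .025/3 in each, and state that the bounds are one-sided 99.17%. Because this loosens a prespecified threshold about tenfold, the sponsor should confirm the intent and date the correction before anyone sees outcome data by arm. The cost is two corrected figures; 152, 174 and 326 need no change on this account. Whether the allowance for dropout is adequate is a different question and is not judged here.

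If .0008 was truly intended, the fraction and the sample size are wrong instead, and the same steps lead to 110 per cell before inflation and about 472 in total.

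A separate clarification, not required by this correction: the treatment contrast is estimated at post-intervention and also "on the effect of treatment condition on the intercept parameter when the model is centered on month 6". The sponsor should state which time point the three primary analyses use. The plan does not say that success at either one would count, but if it did, six bounds at .0083 would allow familywise error up to 6 × .00833 = .05.

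### The sample-size chain 152 → 174 → 326 does not follow from its stated inputs under any single convention, so the power that 326 delivers depends on an unstated reading

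*Combined protocol and SAP*

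**What the plan says.** All of this is in the combined protocol and SAP, under Sample Size Determination for Proposed Analyses.

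- Target: "The power analysis was calculated to be powered at 90"%, with a "Bonferroni-corrected 1-tailed α = .0008 (.025/3 primary outcomes").
- Effect and margin: "Thus, we conducted our power analysis with a conservative expected d of 0.60"; the margin is "here prespecified as Δ d = 0".
- Allocation: "Veterans will be randomly assigned (1:1) to the G-TBT and G-DST conditions".
- Before clustering: "we determined that 152 participants (76 per cell) would be needed".
- After clustering, with an intraclass coefficient of .025 from the pilot: "an estimated 174 participants would be needed to adjust for potential clustering effects if groups average 8 participants".
- Attrition: "We adjusted the sample size upward 37% to adjust for potential discontinuation and 27% based on observed missing data for telehealth assessments", which brings the total to 326 (163 per cell).

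The clustering adjustment is attributed to a cited source and no formula is printed. The attrition sentence does not say whether each percentage multiplies the sample size or divides it as N/(1 − loss). The section on the G-DST control condition sets 6 to 12 participants for a group to begin. The sample-size section does not say whether its average of 8 refers to that starting size or to the members who are analysed.

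**The concern.** The figures 174 and 326 carry the stated 90% power. A reader who applies the usual design effect to the printed inputs does not get 174. A reader who applies the two attrition percentages in the same way, whichever way that is, does not get 326.

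The attrition step matters more. A discontinuation figure of 37% could be an expected proportion lost, or it could be the inflation that offsets a 27% loss, since 1/.73 = 1.37. These are different planning assumptions and give different power. Discontinuation is also a feasibility outcome under Primary Aim 2, and the DSMB reviews retention, so the expected rate should be readable from the plan.

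**Working it through.** **Inputs.** One-sided α = .025/3 = .00833 (z = 2.394), power 90% (z = 1.282), d = 0.60, margin 0, 1:1 allocation, ICC .025, groups of 8, and percentages of 37% and 27%. All come from the sample-size section. I use .025/3 and not the printed .0008 because only the former reproduces 152. I take d = 0.60 as the between-arm difference, because that is how it works in the calculation when the margin is 0.

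**Step 1: reproduce 152.**
n per cell = 2 × [(2.394 + 1.282)/0.60]² = 75.05, rounded up to 76, or 152 in total. Reproduced; power at 76 per cell is 90.4%. At α = .0008, 76 per cell would give 70.6%.

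**Step 2: clustering.**
Design effect = 1 + (8 − 1) × .025 = 1.175.
152 × 1.175 = 178.6, so 179 (180 for equal cells), against the printed 174.

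- Starting from the unrounded 150.1 gives 176.4, so rounding does not explain 174.
- 174/152 = 1.1447. This needs groups of 6.8 at ICC .025, or an ICC of .0207 at groups of 8.
- Equally, 174/1.175 = 148.1, a starting size that the plan does not give.

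Power = Φ(0.60 × √(n/2) − 2.394), where n is the effective number per cell:

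- 174/1.175 = 148.1 effective: 89.6%.
- 179/1.175 = 152.3 effective: 90.5%.

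**Step 3: attrition, from 174.**

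| Convention | Calculation | Result |
|---|---|---|
| Both multipliers | 174 × 1.37 × 1.27 | 302.7 |
| Both losses | 174/(.63 × .73) | 378.3 |
| 37% multiplier, 27% loss | 174 × 1.37/.73 | 326.5 |

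Only the mixed route gives 326. Because 1/.73 = 1.37, it is numerically the same as two 27% losses: 174/.73² = 326.5.

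**Step 4: power with 326 enrolled.** Column A keeps the design effect at 1.175, so 8 is the analysed group size. Column B takes 8 as the starting size, shrinks it by the same factors, and recomputes the design effect on the members left.

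| Reading of 37% and 27% | Analysable | A: power | B: members, design effect, power |
|---|---|---|---|
| Both multipliers | 326/(1.37 × 1.27) = 187.4 | 91.8% | 8/(1.37 × 1.27) = 4.6; 1.090; 93.8% |
| 27% loss twice | 326 × .73² = 173.7 | 89.5% | 8 × .73² = 4.3; 1.082; 92.1% |
| 37% loss, then 27% loss | 326 × .63 × .73 = 149.9 | 84.0% | 8 × .63 × .73 = 3.7; 1.067; 87.8% |

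Column B uses the whole numbers 187, 174 and 150; unrounded inputs change it by no more than 0.1 point. Every row assumes independent losses and no information from incomplete participants.

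**Step 5: carry 179 forward.** Two multipliers: 179 × 1.37 × 1.27 = 311.4, so 312, which 326 covers. The mixed route: 179 × 1.37/.73 = 335.9, so 336, which 326 does not quite cover.

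**The case against.** The strongest reply is that little is at stake. The clustering slip is 5 participants, or 2.9% of 174, and leaves power 0.4 points under target. The adjustment is attributed to an outside source and its formula is not shown, so calling 174 wrong assumes the usual design effect. The figure 326 can be reached from 174, so that step is unclear wording and not failed arithmetic. This stands as to size. It does not remove the point, because the printed ICC and group size still do not lead to 174, and no consistent use of the two percentages leads to 326.

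A reader might infer that the trial does not have its 90% power. The documents do not support that. With two multipliers, 326 gives 91.8% and covers the corrected 179. With two 27% losses, it gives 92.1% if 8 is the starting group size. Only 37% as a true loss falls short on both group-size bases. That calculation is pessimistic: the Missing Data section analyses everyone randomized, uses multiple imputation and keeps non-adherers in the study, and the primary model uses repeated measures with baseline adjustment. Stopping treatment is not the same as losing the outcome.

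A reader might also infer that d = 0.60 cannot be called conservative because the cited range starts at 0.56. That is largely a matter of preference: 0.60 lies below the only Veteran estimate given (0.63), and 0.56 is disclosed in the same paragraph.

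Finally, a revised power figure could suggest false precision, because the printed α of .0008 has a larger effect: 174 clustered participants give about 69% at that level. That stands, and it is why any restated power must name its α.

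**Conclusion.** The point holds as a documentation and arithmetic fault in figures that the trial relies on. The value 174 should be 179 under the usual design effect, at a cost of under half a point against the 90% target. The value 326 mixes two conventions in one sentence, and the possible readings run from 84.0% to 91.8% power at a design effect of 1.175, or from 87.8% to 93.8% if 8 is the starting group size. The shortfall is material, about 2 to 6 points below 90%, only if 37% is the expected proportion discontinuing.

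These figures rest on one-sided .025/3, d = 0.60 as the between-arm difference, the normal formula, independent losses, and no information from incomplete participants. They say nothing on whether 0.60 is a justified between-arm difference with a margin of 0, which is a separate question. This should be corrected; it does not show that the trial is underpowered.

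**What to change.** Revise the one paragraph in the sample-size section:

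1. Print the clustering formula and replace 174 with 179 (180 for equal cells). If the cited source uses a different formula, print that formula and the inputs that give 174.
2. Express 37% and 27% in one convention. If a 27% loss at each stage was meant, say so and show N = n/[(1 − .27)(1 − .27)].
3. State whether 8 is the starting or the analysed group size.
4. Correct the printed .0008 to .025/3 = .0083, here and under Non-Inferiority Analyses (Primary Aim 1), where it is repeated.
5. Keep 326 and restate the power that follows from these choices at that α. If 37% is the expected discontinuation proportion, the 90% must come down to about 84% to 88%, with the note that this gives no credit for partial data.

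The cost is wording and arithmetic. No extra enrolment is needed. The stated power may become slightly less favourable, depending on the answers to items 2 and 3.

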All assessment and treatment providers will be trained and supervised by the Principal Investigator, who is a licensed psychologist (and with backup supervision coverage from [name], licensed psychologist). At intake, participants identified by clinical interview with suicidal ideation and acute intent will be excluded from the study and immediately offered emergency psychiatric care at the VAMC. During the duration of the study, the Principal Investigator (or covering Co-Investigator) will immediately contact the participant and assess suicide risk when any instance of suicide risk is identified (preferably before the participant leaves the appointment). If suicidal ideation is present but not intent, the participant will be retained in the study and reassessed for suicide risk by the investigators in one week. In cases of acute suicidal intent, state law requires immediate hospitalization and these guidelines will be followed.

Assessment of Quality of Life, Psychological Well-Being, Social Reintegration, Psychiatric Symptomatology, and Treatment Satisfaction

The battery of self-report questionnaires and a diagnostic interview will be completed pre-, mid-, and post-treatment and at the 6-month follow-up to track participants' progression through treatment and maintenance. The mid-treatment assessment will include the self-report questionnaires only (no diagnostic interview). Following the initial assessment at pre-treatment, all assessment sessions will be completed either in-person and via VA-approved telehealth technologies, based upon the preference of the participant. These time points for the assessments are consistent with CBT research with Veterans with depressive/anxiety disorders, as well as with the Pl's CDA. Participants will be compensated \$40 for pre-treatment, \$60 for mid-treatment, \$80 for post-treatment, and \$120 for 6-month follow-up for completion of assessment procedures for a total of \$300 for the entire study. To reduce the likelihood of missing data, all assessments will be scheduled separately from normal treatment sessions. Assessments of quality of life, social reintegration, and general symptoms of the depressive/anxiety disorders, rather than multiple disorder-specific questionnaires, were chosen due to the

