transdiagnostic approach and related research aims of the proposed study. In addition, participants will be asked to voluntarily solicit a friend or family member to complete a collateral report on a measure of functioning (IIRS). Procedures for adapting and analyzing the collateral report will follow previously published investigations of self-other assessments by the study team ([name] et al., 2010; Simms et al., 2010). All assessments will be completed by the Project Research Recruiter and Assessor. Additional training will be required prior to administration of the diagnostic interview (ADIS-5). The assessor will be required to observe the PI administer the ADIS-5 twice and then administer the ADIS-5 twice themselves under the direct observation of the PI. The assessor will be blinded to treatment condition and supervised by the PI. ADIS-5 assessments will be recorded to investigate inter-rater reliability of diagnoses, with 20% of recordings being re-assessed by an external ADIS-trained assessor after the participant has completed all study procedures, with feedback provided to the assessor throughout the duration of the study to improve reliability. In addition to the four assessment points, select measures (PHQ-9 and PCL-5) will be administered every other treatment session to monitor safety and treatment progress.

Albany Panic and Phobia Questionnaire (APPQ). The APPQ is a 27-item self-report measure that assesses agoraphobia, social anxiety, and interoceptive avoidance (Rapee et al., 1994/1995). Each subscale has been shown to have good internal consistency (α s > .85) and temporal stability (rs > .87) (Brown et al., 2005).

Anxiety Disorder Interview Schedule-5 (ADIS-5). The ADIS-5 is a semi-structured interview designed to assess a wide range of Axis I disorders (Brown, 2014). The ADIS-5 assesses current and past diagnoses with DSM diagnostic criteria, severity scores, and lists of feared and avoided situations for the anxiety disorders. The ADIS-5 has demonstrated excellent inter-rater reliability and validity of depressive/anxiety disorder diagnoses.

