The full intent-to-treat (ITT) analysis set will comprise all randomized participants. Missing data in the full analysis set will occur if participants discontinue treatment prior to the end of the study or do not complete an outcome measure. Participants will not be discontinued from the study because of non-adherence and all will remain in the study unless consent is withdrawn or if there are concerns regarding participant safety. Missing data for the ITT analysis set will be imputed using multiple imputation (MI) methods, which are superior to most alternative missing data approaches even when data is missing completely at random (MCAR) or missing at random (MAR; Schafer & Graham, 2002; Enders, 2010). Although the use of MI will result in the least biased parameters, regardless of data missingness, several approaches will be undertaken to better understand the exact mechanisms for missing data. Little's (1988) MCAR test will be applied to all final models to determine whether data can be considered MCAR. Further, the results of analyses using study completers and protocol adherers (completer and per-protocol analyses) will be compared with results using the ITT analysis set to test sensitivity of study conclusions to study discontinuations and protocol non-adherence. Baseline differences also will be explored between treatment completers and those that discontinue. If baseline differences are detected, these covariates will then be included in the final model as auxiliary variables to improve the plausibility of assuming data is MAR (Collins et al., 2001; Enders, 2010; Graham, 2003;). Finally, discontinuation proportion will be used as one of the outcome measures of intervention feasibility.

Non-Inferiority Analyses (Primary Aim 1)

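### An undefined safety concern can end study participation rather than only study treatment, and no outcome assessment is provided for afterwards: a minor gap that is cheap to close

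*Combined protocol and SAP*

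**What the plan says.** The Missing Data section defines the ITT set as all randomized participants. It rules out discontinuing anyone for non-adherence and then states that "all will remain in the study unless consent is withdrawn or if there are concerns regarding participant safety". What is left is the study, not the treatment. Safety concerns are not defined there.

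Missing outcomes in the ITT set are multiply imputed. Baseline variables that differ between completers and those who discontinue are to be "included in the final model as auxiliary variables to improve the plausibility of assuming data is MAR". Completer and per-protocol analyses serve as sensitivity analyses.

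The section on suicidal ideation or intent is more specific: "If suicidal ideation is present but not intent, the participant will be retained in the study". Acute intent leads to hospitalization. That section does not say that hospitalization ends participation, nor what happens to later assessments.

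The assessment section sets out pre-, mid- and post-treatment and 6-month assessments. It adds that "To reduce the likelihood of missing data, all assessments will be scheduled separately from normal treatment sessions", and that after the first one "all assessment sessions will be completed either in-person and via VA-approved telehealth technologies, based upon the preference of the participant". It also says that "select measures (PHQ-9 and PCL-5) will be administered every other treatment session to monitor safety and treatment progress".

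The Non-Inferiority Analyses section reads the treatment effect at post-intervention and at month 6, against a margin of d = 0.

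**The concern.** In a depression and PTSD trial, a participant removed on safety grounds has plausibly worsened on the quantities that the primary outcomes measure (IIRS, PCL-5, DASS depression). If removal also ends assessment, the scores lost are the post-treatment and month-6 values on which the primary comparison rests. Imputation under MAR would then tend to give these participants scores like those of otherwise similar participants who stayed, and so probably too favourable.

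If removals differ between arms, the arm with more of them looks somewhat better than it is. With the margin at zero, no tolerance is available to absorb such a shift. ITT inclusion keeps the person in the analysis but does not observe the score. The completer and per-protocol analyses do not recover it either.

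**Working it through.** **1. Search for a rule on assessment after a safety exit.**

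- Randomization Procedures: guarantees inclusion in the ITT analysis and is silent on data collection after exit.
- Safety Measures: retains ideation without intent, hospitalizes acute intent, and is silent on later outcome assessment.
- Assessment section: gives the general schedule, with no provision for removed participants. The every-other-session PHQ-9 and PCL-5 are tied to treatment sessions, so they presumably stop when sessions stop.
- Missing Data: names safety as a ground for leaving and covers the loss by imputation.
- Non-Inferiority and Feasibility analyses: no rule on collecting scores after exit.

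No section supplies the rule. Consent pages are not in the file, so this holds for the visible text only.

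**2. The plan's sample size.** Inputs from Sample Size Determination: d = 0.60, margin 0, power 90%, one-sided alpha printed as .0008 and also as .025/3 = .0083.

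- n per arm = 2 × (z for alpha + z for power)² / d².
- At .0083: 2 × (2.394 + 1.282)² / 0.36 = 75.1, so 76 per arm and 152 in all, as stated.
- At .0008: 109.4, so 110 per arm and 220 in all, which does not match. Both alphas are carried below.
- Design effect for groups of 8 with intraclass correlation .025: 1 + 7 × .025 = 1.175. 152 × 1.175 = 178.6, against the stated 174.
- 174 × 1.37 / (1 − 0.27) = 326.5, against the stated 326.

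The allowances for discontinuation and missing assessments protect numbers. They do not protect against bias.

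**3. Illustrative bias.** The documents give no removal rate, so these inputs are assumptions: 5% removed in one arm and 2% in the other (8.2 and 3.3 of 163), and a gap of 0.3 to 1.0 SD between true and imputed scores, equal in both arms.

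- Bias in d = difference in removal proportion × gap: 0.03 × 0.3 = 0.009; 0.03 × 1.0 = 0.03.
- SE of d = √(2 × 1.175 / 163) = 0.120, ignoring baseline adjustment and other missing data.
- Bias / SE = 0.075 to 0.25.
- If only 87 per arm give data (174 / 2), SE = √(2 × 1.175 / 87) = 0.164 and bias / SE = 0.05 to 0.18.

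**4. Chance of a false claim per outcome when true d = 0**, computed as 1 − Φ(z for alpha − bias/SE) with SE 0.120, if G-TBT loses more:

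| Alpha | No bias | Bias 0.009 | Bias 0.03 |
|---|---|---|---|
| .0008 | .0008 | .0010 | .0018 |
| .025/3 | .0083 | .0102 | .0160 |

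If G-DST loses more, the chance falls below the nominal value. If rates and gaps are equal in both arms, there is no bias.

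**5. Would an imbalance show?** Fisher's exact test for 8 v 3 of 163 per arm gives p = .22, so a test on safety exits alone would not flag it.

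**6. What collecting the scores could recover.** The plan cites "27% based on observed missing data for telehealth assessments". If 27% of the offered assessments are still missed, 0.73 of the bias is removed: 0.0066 to 0.022 in d. If half are missed (assumption), 0.0045 to 0.015.

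**The case against.** The strongest case against is that the point is immaterial. Every driver of the calculation is assumed. The result is small next to the d of 0.60 used for sizing, and only part of it can be recovered. The 1.0 SD end is severe for a gap that remains after imputation, since earlier scores exist. The trigger is narrow: recent suicide attempts and acute intent are excluded at entry, non-adherence removes nobody, and ideation without intent is retained. All of this stands, and it sets the weight of the point.

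Oversight also counts. The Feasibility section tabulates reasons for discontinuation, which could reveal an 8 v 3 split whatever a test shows. The internal committee reviews adverse effects at least quarterly. The DSMB reviews retention, adverse events and changes in self-report scores yearly. These may reveal an imbalance, but they do not supply the missing scores.

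The primary model covaries the baseline value, and its listed covariates end "and number of treatment sessions) will be added to the model to adjust for putative confounding variables". That may narrow the gap. The plan does not say whether the imputation uses the session count or the scores before removal. That question concerns all missing data, not safety exits in particular, and adds no weight here.

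A reader might infer that every participant who becomes suicidal or is hospitalized is lost to follow-up. The documents do not support this: the safety section keeps ideation without intent in the study and never says that hospitalization ends participation. A hospitalized participant who is not removed stays on the ordinary schedule.

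**Conclusion.** The point holds on the text, as a minor one. A safety concern can end participation, the term is undefined, and the visible plan makes no provision for later outcome scores. Under assumed removals of 5% v 2% and a gap of 0.3 to 1.0 SD, the bias in d is about 0.01 to 0.03, or 0.07 to 0.25 standard errors. Those rates and gaps come from no document, so the figures illustrate scale and are not estimates.

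A reader might infer that the comparison is tilted towards G-TBT or that the non-inferiority conclusion is unsafe. The documents support neither: no rates are given, the direction is unknown, and equal losses cancel. The reason to act is that the change is cheap and that scores not collected cannot be recovered later.

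**What to change.** In the Missing Data section, state that:

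- a safety concern may stop study treatment but does not by itself end outcome follow-up;
- the remaining scheduled self-report assessments (post-treatment and 6-month) are still offered, by telehealth if preferred, unless consent is withdrawn;
- the clinician may delay or omit an individual assessment on safety grounds, with the reason recorded;
- scores so collected enter the ITT analysis.

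The third item keeps clinical discretion over the single assessment without turning it into removal from the study. The suicide-risk procedure stays as written.

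The cost is mainly wording, since assessments are already scheduled apart from therapy and telehealth is already allowed. Because it alters what is asked of participants after a safety event, it would need ethics review and some coordination with clinical staff for people in crisis. Recovery will be partial, as some will decline or need a delayed assessment.
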